8.1.1. Primary Efficacy Assessment

The integrated Alzheimer's Disease Rating Scale (iADRS) assesses the impact of cognitive loss on the ability to conduct everyday activities and provides a measure of global AD severity as a single summary score. The iADRS comprises 2 underlying domains ("cognitive ability" and "functional ability"), with each representing related but separate concepts. The iADRS integrates the items that make up both domains into a single overall score that is conceptually distinct from

either domain assessed individually. The combination score of the iADRS captures commonalities across its domains, minimizing noise that exists within each domain individually. The iADRS captures clinical progression from MCI due to AD through moderate dementia due to AD, and treatment effects have been demonstrated across MCI and mild dementia due to AD (Honig et al. 2018; Wessels et al. 2020; Mintun et al. 2021). The iADRS has been validated (Wessels et al. 2015, 2018) and its statistical properties have been described. Minimal clinically important change estimates for the iADRS have been defined (Wessels et al. 2022b) and associations with meaningful outcomes of disease such as caregiver burden and quality of life have been demonstrated (Wessels et al. 2022a).

The ADAS-Cog13 and the ADCS-ADL will be the actual scales administered to participants.

8.1.2. Secondary Efficacy Assessments

8.1.2.1. MMSE

The Mini-Mental State Examination (MMSE) is a brief instrument used to assess cognitive function in participants (Folstein et al. 1975). The instrument measures orientation, memory, and attention; the ability of the participant to name objects; follow verbal and written commands; write a sentence; and copy figures. The range for the total MMSE score is 0 to 30, with lower scores indicating greater level of impairment. The MMSE should whenever possible be administered by the same rater from visit to visit to reduce potential variability.

8.1.2.2. ADAS-Cog₁₃

The Alzheimer's Disease Assessment Scale – Cognitive subscale (ADAS-Cog₁₃) is a rater-administered instrument that was designed to assess the severity of dysfunction in the cognitive and noncognitive behaviors characteristic of persons with AD (Rosen et al. 1984). The ADAS-Cog₁₃ should, whenever possible, be administered by the same rater from visit to visit to reduce potential variability.

The cognitive subscale of the ADAS, the ADAS-Cog₁₃, consists of 13 items assessing areas of cognitive function that are the most typically impaired in AD: orientation, verbal memory, language, praxis, delayed free recall, digit cancellation, and maze-completion measures (Mohs et al. 1997). The ADAS-Cog₁₃ scale ranges from 0 to 85, with higher scores indicating greater disease severity.

8.1.2.3. CDR

The CDR (Hughes et al. 1982; Morris 1993) is a global assessment tool that can be used to effectively evaluate both cognition and function. The tool was initially developed to measure dementia severity and covers 6 categories or “boxes”: Memory, Orientation, Judgment and Problem Solving, Community Affairs, Home and Hobbies, and Personal Care.

The CDR global ratings, calculated using an algorithm, range from 0 (no dementia) to 3 (severe dementia) while CDR-SB scores, calculated by adding the box scores, range from 0 to 18 (with higher scores indicative of more impairment). Scoring is determined by a clinician through a semi-structured and in-depth interview with both the affected individual and their study partner. This scale demonstrates acceptable psychometric characteristics (Coley et al. 2011; Cedarbaum

et al. 2013) and has been shown to be sensitive enough to detect disease progression, even in populations with less advanced clinical disease (Williams et al. 2013; Wessels et al. 2015).

The CDR should be administered whenever possible by the same rater from visit to visit to reduce potential variability. The participant's memory, orientation, judgment, and problem-solving ability are assessed. The study partner and participant must be interviewed separately.

Note: The CDR may be administered to the participant and/or study partner by phone. Regardless of administration method, the CDR must be administered to the study partner prior to the participant. While the participant may complete the CDR by phone, other procedures and assessments may be required in person, as described in the SoA (Section 1.3).

8.1.2.4. ADCS-ADL

The ADCS-ADL is a 23-item inventory developed as a rater-administered questionnaire that is to be answered by the participant's study partner (Galasko et al. 1997, 2004). The ADCS-ADL should be administered by the same rater from visit to visit to reduce potential variability.

The ADCS-ADL subset of items (items 6a and 7 to 23) for iADLs will be used as a secondary efficacy measure. The focus in the early symptomatic AD population is on the iADLs rather than the basic Activities of Daily Living (bADLs), which are thought to be affected in more severe stages of the disease. The range for the iADL score is 0 to 59, with lower scores indicating greater disease severity.

For each of the specific items, the study partner is first asked if the participant attempted the ADL during the past 4 weeks. If the participant did attempt the ADL, the study partner is asked to rate the participant's performance level based on a set of performance descriptions. Scores for each item and the overall score for the tool are calculated. The range for the total ADCS-ADL score is 0 to 78, with lower scores indicating greater level of impairment. Separate scores for the bADLs (0 to 19) will also be computed.

8.1.2.5. Biomarker Efficacy Measures

Florbetapir F18 PET scan

Change in amyloid burden (as assessed by florbetapir F18 PET) will be compared in donanemab- and placebo-treated participants.

Flortaucipir F18 PET scan

Change in tau pathology (as assessed by flortaucipir F18 PET) will be compared in donanemab- and placebo-treated participants.

Volumetric MRI

Volumetric magnetic resonance imaging (vMRI) of the brain will be performed according to the SoA (Section 1.3). Donanemab- and placebo-treatment effects on vMRI will be assessed and compared to evaluate the loss of brain volume that occurs in AD participants.

8.2. Safety Assessments

Planned timepoints for all safety assessments are provided in the SoA (Section 1.3).

8.2.1. Physical and Neurological Examinations

Complete and brief physical examinations will be performed as indicated in the SoA (Section 1.3).

The complete physical examination will include assessment of the following:

- general appearance;
- skin, head, and neck;
- lymph nodes;
- thyroid;
- abdomen (bowel sounds, liver and spleen palpation);
- back (costovertebral angle tenderness); and
- musculoskeletal, cardiovascular, and respiratory systems.

The brief physical examination will include assessments of the following:

- skin,
- lungs,
- cardiovascular system, and
- abdomen (bowel sounds, liver and spleen palpation).

Complete neurological examinations will be performed as indicated in the SoA (Section 1.3).

The examinations will include a thorough assessment of the following:

- gait,
- balance,
- coordination,
- cranial nerves,
- sensory and motor systems, and
- reflexes.

If necessary, given the training of the PI, a neurologist may be consulted in the event of significant new findings.

If a clinically meaningful change in a MRI is noted during the study, an additional full neurological exam should be performed as soon as possible, along with any other medical follow-up deemed necessary by the investigator.

8.2.2. Vital Signs

Vital signs, including temperature, will be measured at all visits.

Vital signs should be taken before administration of IP. Vital signs may be repeated as needed.

8.2.2.1. Blood Pressure

Sitting blood pressure and pulse will be measured after 5 minutes in the sitting position at all visits. In addition, orthostatic blood pressure and pulse will be measured supine and standing at designated visits, as detailed in the SoA (Section 1.3).

For orthostatic blood pressure monitoring, participants should be supine for at least 5 minutes and then stand for at least 3 minutes prior to taking the respective measurements. If the subject feels unable to stand, only supine vital signs will be recorded.

Unscheduled orthostatic vital signs should be assessed, if possible, during any AE of dizziness or posture-induced symptoms.

Any clinically significant findings from vital sign measurements that result in a diagnosis and that occur after the participant receives the first dose of study treatment should be reported to Lilly or its designee as an AE via CRF/electronic data entry.

8.2.2.2. Height, Weight, and Body Temperature

Height and body weight will be measured. Measurements should be taken, when possible, with the same scale for all measurements. Body mass index will be calculated from the height and body weight.

Temperature will be recorded using an oral or tympanic (or other acceptable route) thermometer.

Any body weight data entered into the CRF will be used for the overall data analysis

8.2.3. Electrocardiograms

For each participant, 12-lead digital ECGs will be collected during the double-blind period, according to the SoA (Section 1.3). Participants must be supine for approximately 5 to 10 minutes before ECG collection and remain supine but awake during ECG collection.

Electrocardiograms may be obtained at additional times, when deemed clinically necessary. Collection of more ECGs (replicates) than expected at a timepoint is allowed when needed to ensure high-quality records.

Electrocardiograms will initially be interpreted by a qualified physician (the investigator or qualified designee) at the site as soon after the time of ECG collection as possible, and ideally while the participant is still present, to determine whether the subject meets entry criteria at the relevant visit(s) and for immediate participant management, should any clinically relevant findings be identified.

After enrollment, if a clinically significant increase in the QT/corrected QT (QTc) interval from baseline or other clinically significant quantitative or qualitative change from baseline is identified, the participant will be assessed by the investigator for symptoms (e.g., palpitations, near syncope, syncope) and to determine whether the participant can continue in the study. The investigator or qualified designee is responsible for determining if any change in participant management is needed. The investigator or qualified designee must document his/her review of the ECG printed at the time of evaluation.

All digital ECGs will be electronically transmitted to a designated central ECG laboratory. A cardiologist at the central ECG laboratory will then conduct a full overread. A report based on

data from this overread will be issued to the investigative site. These data are not routinely reported back to the investigative site. All data from the overreads will be placed in the Lilly database for analytical and study report purposes.

When there are differences in ECG interpretation between the investigator (or qualified designee) and the cardiologist at the central ECG laboratory, the investigator's (or qualified designee's) interpretation will be used for study entry and immediate participant management. Interpretations from the cardiologist at the central ECG laboratory will be used for data analysis and report writing purposes.

The investigator (or qualified designee) must document his/her review of the ECG printed at the time of collection, the final overread ECG report issued by the central ECG laboratory, and any alert reports.

8.2.4. Clinical Safety Laboratory Assessments

See Section 10.2 for the list of clinical laboratory tests to be performed and to the SoA for the timing and frequency.

The investigator must review the laboratory results, document this review, and report any clinically relevant changes occurring during the study in the AE section of the CRF. The laboratory reports must be filed with the source documents. Clinically significant abnormal laboratory findings are those which are not associated with the underlying disease, unless judged by the investigator to be more severe than expected for the participant's condition.

All laboratory tests with values considered clinically significantly abnormal during participation in the study, or within the follow-up period after the last dose of IP, should be repeated until the values return to normal, baseline, or are no longer considered clinically significant by the investigator or medical monitor.

1. If such values do not return to normal/baseline within a period of time judged reasonable by the investigator, the etiology should be identified and the sponsor notified.
2. All protocol-required laboratory assessments, as defined in Section 10.2, must be conducted in accordance with the SoA and laboratory manual (or standard collection requirements, if applicable).
3. If laboratory values from non-protocol-specified laboratory assessments performed at an investigator-designated local laboratory require a change in participant management or are considered clinically significant by the investigator (for example, SAE, AE, or dose modification), then the results must be recorded in the CRF. Laboratory results from this laboratory must be retained with source documents unless a Source Document Agreement or comparable document cites an electronic location that accommodates the expected retention duration.

With the exception of laboratory test results that may unblind the study, Lilly or its designee will provide the investigator with the results of laboratory tests analyzed by a central vendor, if a central vendor is used for the clinical trial.

Any clinically significant findings from laboratory tests that result in a new diagnosis and that occur after the participant receives the first dose of IP should be reported to Lilly or its designee as an AE via CRF/electronic data entry.

8.2.5. Magnetic Resonance Imaging

Magnetic resonance imaging of the brain will be performed according to the SoA (Section 1.3) and as clinically indicated. Unscheduled MRIs may be performed at the discretion of investigator.

This technology will be used to check for evidence of ARIA-H or ARIA-E, and other clinically relevant inclusion/exclusion and safety findings (vMRI will also be used to calculate brain volumes, as noted in Section 9.4.4).

The MRI scans will be reviewed by the investigator or qualified designee for immediate participant management. Any clinically significant findings noted at baseline that result in a diagnosis should be recorded as a preexisting condition or AE. After the MRI scan is read locally, the MRI scans will be sent for analysis to a centralized MRI vendor designated by Lilly. Final MRI eligibility at screening will be determined by the centralized MRI vendor designated by Lilly and the MRI results will be reported to the site as “does” or “does not” meet MRI eligibility criteria.

Specific analyses of the scans, including assessments of ARIA-H and ARIA-E and calculations of brain volumes, will be interpreted by the centralized MRI vendor for data analysis and report writing purposes.

Results of centrally read MRIs regarding participant care/safety will be reported back to sites.

8.2.6. Hepatic Safety Monitoring

Close Hepatic Monitoring

Laboratory tests (Section 10.4), including ALT, AST, ALP, TBL, direct bilirubin, gamma-glutamyl transferase (GGT), and creatine kinase (CK), should be repeated within 48 to 72 hours to confirm the abnormality and to determine if it is increasing or decreasing, if 1 or more of these conditions occur:

If a participant with baseline results of ...	develops the following elevations:
ALT or AST <1.5x ULN	ALT or AST ≥3x ULN
ALP <1.5x ULN	ALP ≥2x ULN
TBL <1.5x ULN	TBL ≥2x ULN (except for participants with Gilbert's syndrome)
ALT or AST ≥1.5x ULN	ALT or AST ≥2x baseline
ALP ≥1.5x ULN	ALP ≥2x baseline
TBL ≥1.5x ULN	TBL ≥2x baseline (except for participants with Gilbert's syndrome)

Abbreviations: ALP = alkaline phosphatase; ALT = alanine aminotransferase; AST = aspartate aminotransferase; TBL = total bilirubin level; ULN = upper limit of normal.

If the abnormality persists or worsens, clinical and laboratory monitoring, and evaluation for possible causes of abnormal liver tests should be initiated by the investigator in consultation with the Lilly-designated medical monitor. At a minimum, this evaluation should include physical examination and a thorough medical history, including symptoms, recent illnesses (for example, heart failure, systemic infection, hypotension, or seizures), recent travel, history of concomitant medications (including over-the-counter), herbal and dietary supplements, and history of alcohol drinking and other substance abuse.

Initially, monitoring of symptoms and hepatic biochemical tests should be done at a frequency of 1 to 3 times weekly, based on the participant's clinical condition and hepatic biochemical tests. Subsequently, the frequency of monitoring may be lowered to once every 1 to 2 weeks, if the participant's clinical condition and laboratory results stabilize. Monitoring of ALT, AST, ALP, and TBL should continue until levels normalize or return to approximate baseline levels.

Comprehensive Hepatic Evaluation

A comprehensive evaluation should be performed to search for possible causes of liver injury if 1 or more of these conditions occur:

If a participant with baseline results of...	develops the following elevations:
ALT or AST <1.5x ULN	ALT or AST \geq 3x ULN with hepatic signs/symptoms*, or ALT or AST \geq 5x ULN
ALP <1.5x ULN	ALP \geq 3x ULN
TBL <1.5x ULN	TBL \geq 2x ULN (except for participants with Gilbert's syndrome)
ALT or AST \geq 1.5x ULN	ALT or AST \geq 2x baseline with hepatic signs/symptoms*, or ALT or AST \geq 3x baseline
ALP \geq 1.5x ULN	ALP \geq 2x baseline
TBL \geq 1.5x ULN	TBL \geq 1.5x baseline (except for participants with Gilbert's syndrome)

Abbreviations: ALP = alkaline phosphatase; ALT = alanine aminotransferase; AST = aspartate aminotransferase; TBL = total bilirubin level; ULN = upper limit of normal.

* Hepatic signs/symptoms are severe fatigue, nausea, vomiting, right upper quadrant abdominal pain, fever, rash, and/or eosinophilia >5%.

At a minimum, this evaluation should include physical examination and a thorough medical history, as outlined above, as well as tests for Prothrombin time and INR; tests for viral hepatitis A, B, C, or E; tests for autoimmune hepatitis; and an abdominal imaging study (for example, ultrasound or computed tomography [CT] scan).

Based on the participant's history and initial results, further testing should be considered in consultation with the sponsor-designated medical monitor, including tests for hepatitis D virus, cytomegalovirus, Epstein-Barr virus, acetaminophen levels, acetaminophen protein adducts, urine toxicology screen, Wilson's disease, blood alcohol levels, urinary ethyl glucuronide, and serum phosphatidylethanol. Based on the circumstances and the investigator's assessment of the participant's clinical condition, the investigator should consider referring the participant for a hepatologist or gastroenterologist consultation, magnetic resonance cholangiopancreatography, endoscopic retrograde cholangiopancreatography, cardiac echocardiogram, or a liver biopsy.

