21. Screening MRI which shows evidence of significant abnormality that would suggest another potential etiology for progressive dementia or a clinically significant finding that may impact the participant's ability to safely participate in the study.
22. Have any contraindications for MRI, including claustrophobia or the presence of contraindicated metal (ferromagnetic) implants/cardiac pacemaker.
23. Have a centrally read MRI demonstrating presence of ARIA-E, >4 cerebral microhemorrhages, more than 1 area of superficial siderosis, any macrohemorrhage or severe white matter disease at screening.
24. Sensitivity to florbetapir F18 or flortaucipir F18.
25. Poor venous access.
26. Contraindication to PET.
27. Present or planned exposure to ionizing radiation that, in combination with the planned administration of study PET ligands, would result in a cumulative exposure that exceeds local recommended exposure limits.
28. Alanine aminotransaminase (ALT) $\geq 2.5X$ the upper limit of normal (ULN) of the performing laboratory, aspartate aminotransferase (AST) $\geq 2.5X$ ULN, total bilirubin level (TBL) $\geq 1.5X$ ULN, or alkaline phosphatase (ALP) $\geq 2X$ ULN at screening.

Note: Participants with TBL $\geq 1.5X$ ULN are not excluded if they meet all of the following criteria for Gilbert syndrome:

- Bilirubin is predominately indirect (unconjugated) at screening (direct bilirubin within normal limits).
- Absence of liver disease.
- ALT, AST, and ALP $\leq 1X$ ULN at screening.
- Hemoglobin is not significantly decreased at screening.

Prior/Concomitant Therapy

29. Have had prior treatment with a passive anti-amyloid immunotherapy <5 half-lives prior to randomization.
30. Have received active immunization against A β in any other study.
31. Have known allergies to donanemab, related compounds, or any components of the formulation.

Prior/Concurrent Clinical Study Experience

32. Are currently enrolled in any other interventional clinical trial involving an IP or any other type of medical research judged not to be scientifically or medically compatible with this study.

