7.1. Discontinuation of Study Intervention

Investigational product may be discontinued for a participant for the following reasons (details given below):

- By request of the participant or participant's designee (for example, legal guardian)
- Clinical judgment
- A hepatic event or liver test abnormality
- C-SSRS results
- ECG finding
- ARIA
- Systemic hypersensitivity reaction
- Severe noncompliance
- The participant requires an excluded therapeutic agent

In rare instances, it may be necessary for a participant to permanently discontinue (definitive discontinuation) IP. If IP is definitively discontinued, the participant will remain in the study (following the SoA, except as noted below) to be evaluated for safety and efficacy.

If IP infusion is permanently discontinued and the participant remains in the study. See Section 8.5 for PK sampling instructions. Participants who require a ferromagnetic implant or insertion of a cardiac pacemaker that is not MRI compatible will be permanently discontinued from IP and are not to have further MRIs.

Clinical Judgment

Adverse event or clinically significant laboratory value, ECG result, physical examination finding, MRI finding (such as symptomatic ischemic stroke), C-SSRS result, or vital sign measurement of such severity that, in the opinion of the investigator or sponsor-designated medical monitor, continued treatment is not in the best interest of the participant.

Hepatic Event or Liver Test Abnormality

Participants who are discontinued from IP due to a hepatic event or liver test abnormality should have additional hepatic safety data collected via the CRF.

Discontinuation of the IP for abnormal liver tests **should be** considered by the investigator when a participant meets 1 of the following conditions after consultation with the sponsor-designated medical monitor:

- ALT or AST >8X ULN
- ALT or AST >5X ULN for more than 2 weeks
- ALT or AST >3X ULN and TBL >2X ULN or international normalized ratio (INR) >1.5
- ALT or AST >3X ULN with the appearance of fatigue, nausea, vomiting, right upper-quadrant pain or tenderness, fever, rash, and/or eosinophilia (>5%)

- ALP >3X ULN
- ALP >2.5X ULN and TBL >2X ULN
- ALP >2.5X ULN with the appearance of fatigue, nausea, vomiting, right quadrant pain or tenderness, fever, rash, and/or eosinophilia (>5%)

C-SSRS

In addition, IP may be discontinued if participants:

- Answer “yes” to Question 4 or Question 5 on the “Suicidal Ideation” portion of the C-SSRS, or

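### For eligible participants with raised baseline liver tests, the Section 8.2.6 repeat-test trigger can come later than the Section 7.1 criteria for considering discontinuation

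*Protocol*

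**What the plan says.** Section 5.2 (exclusion 28) excludes "alkaline phosphatase (ALP) $\geq 2X$ ULN at screening", and ALT or AST at or above 2.5x ULN. Participants with ALP of 1.5 to <2.0x ULN, or ALT/AST of 1.5 to <2.5x ULN, can therefore be enrolled.

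Section 8.2.6 has two tables. Close Hepatic Monitoring asks for a repeat panel within 48 to 72 hours. Comprehensive Hepatic Evaluation asks for a search for causes with a minimum set of tests. Each table has one set of rows for baselines below 1.5x ULN, in multiples of ULN, and another for baselines at or above 1.5x ULN, in multiples of baseline. In the second set the ALP entry is "ALP ≥2x baseline" in the repeat table, and the comprehensive table uses the same multiple. The repeat for ALT/AST is also set at twice baseline.

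Section 7.1 asks the investigator to consider stopping study drug "when a participant meets 1 of the following conditions after consultation with the sponsor-designated medical monitor". The criteria are all multiples of ULN. They include ALP above 3x ULN alone, "ALP >2.5X ULN with the appearance of fatigue, nausea, vomiting" (or other listed symptoms) and "ALT or AST >3X ULN with the appearance of fatigue, nausea, vomiting" (likewise). None is adjusted for a raised baseline. Nothing in Section 8.2.6 says that meeting a Section 7.1 criterion also calls for the repeat or the work-up.

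**The concern.** Section 8.2.6 gives the repeat panel the job of confirming an abnormality and showing its direction. That information is wanted when discontinuation is being weighed, so the repeat should be called for no later than the value that opens that discussion. For baselines below 1.5x ULN it is: ALP is repeated from 2x ULN. For raised baselines the order can reverse.

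Without a trigger, the next chemistry panel fixed by the Schedule of Activities may be far off. Panels fall at Weeks 0, 12, 24, 36, 52, 64 and 76, then at Weeks 90, 102, 130 and 154. The gap is thus 12 to 16 weeks in the double-blind period and up to 28 weeks in the extension, while infusions are scheduled every 4 weeks. What is at stake is the timing of safety monitoring. Sample size, power and type I error are untouched.

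**Working it through.** The protocol gives no figure to reproduce. The check converts each trigger to multiples of ULN and compares it with Section 7.1.

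**Inputs (x ULN)**
- Eligible raised baseline *b*: ALP 1.5 to <2.0; ALT/AST 1.5 to <2.5 (Section 5.2 with the 1.5x split in Section 8.2.6).
- Repeat trigger, raised baseline: 2*b* for ALP and for ALT/AST. Below 1.5x: ALP 2.0, ALT/AST 3.0 (Section 8.2.6).
- Comprehensive trigger, ALP: 2*b* for raised baseline; 3.0 below 1.5x (Section 8.2.6).
- Section 7.1 threshold *D*: ALP 3.0 alone or 2.5 with symptoms; ALT/AST 3.0 with symptoms.

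**Formula:** gap = 2*b* − *D*. A positive gap means that values above *D* and below 2*b* meet Section 7.1 while the trigger has not fired.

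**ALP (repeat and comprehensive evaluation, same trigger)**

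| Baseline *b* | Trigger 2*b* | Gap to >3.0 alone | Gap to >2.5 with symptoms |
|---|---|---|---|
| 1.5 | 3.0 | 0.0 | 0.5 |
| 1.6 | 3.2 | 0.2 | 0.7 |
| 1.8 | 3.6 | 0.6 | 1.1 |
| 1.9 | 3.8 | 0.8 | 1.3 |
| 1.99 | 3.98 | 0.98 | 1.48 |

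The trigger is late against ALP alone for every baseline above 1.5x, and against ALP with symptoms for every baseline from 1.5x. Example: ALP going from 1.9 to 3.5 is 3.5/1.9 = 1.84x baseline. It is above 3.0x ULN, so it meets Section 7.1, but it is below twice baseline, so neither step is called for.

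**ALT/AST with symptoms (repeat test, each enzyme read against its own baseline)**

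| Baseline *b* | Trigger 2*b* | Gap to >3.0 with symptoms |
|---|---|---|
| 1.5 | 3.0 | 0.0 |
| 1.8 | 3.6 | 0.6 |
| 2.0 | 4.0 | 1.0 |
| 2.4 | 4.8 | 1.8 |
| 2.49 | 4.98 | 1.98 |

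The repeat is late for every baseline above 1.5x.

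**Where the order is sound**
- ALT/AST above 8x ULN: the repeat starts below 5.0 (2 × 2.5) and the comprehensive evaluation below 7.5 (3 × 2.5), so both come first.
- ALT/AST above 5x for more than 2 weeks: the repeat starts below 5.0, so it comes first.
- Criteria that need bilirubin above 2x ULN: bilirubin at 2x ULN triggers both steps by itself outside Gilbert's syndrome.
- Baseline below 1.5x: the repeat starts at 2.0 for ALP and 3.0 for ALT/AST, no later than any of these thresholds.

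The jump at the split shows the cause. A baseline ALP of 1.49 is retested from 2.0x ULN; a baseline of 1.5 is not retested until 3.0x.

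**The case against.** The best defence is that the two sections do different jobs and can both be followed. Section 7.1 is not a stopping rule, and baseline multiples are a sensible way to avoid retesting people whose values are always somewhat high. The protocol also has fallbacks. Section 8.2.4 asks for clinically significant values to be repeated and for the cause to be found if they do not settle. Section 10.4 lists hepatic tests that may be obtained, and may be required in consultation with the medical monitor. Unscheduled laboratory tests are allowed. This stands as a reason to keep the point small. It does not remove the point, because these provisions depend on judgment and none sets a retest window.

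The ALT/AST part depends on how the rows are read. A participant with raised ALT but AST below 1.5x ULN could be placed in the lower-baseline row as well, and ALT at 3x ULN would then trigger the repeat. On that reading the ALT/AST gap needs both enzymes to be raised. The ALP part does not depend on this.

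A reader might infer more than the documents support:
- **That study drug would be stopped on an unconfirmed value.** Section 7.1 only asks for discontinuation to be considered, after consultation.
- **That the criterion "ALT or AST >3X ULN and TBL >2X ULN or international normalized ratio (INR) >1.5" opens a much wider gap.** It needs an INR result, which is not in the routine panel of Section 10.2. If INR has been measured, further investigation has normally begun.
- **That "ALT or AST >5X ULN for more than 2 weeks" is also missed.** By then the repeat has been triggered, and Section 8.2.6 says that, if the abnormality persists, "evaluation for possible causes of abnormal liver tests should be initiated by the investigator". Only the comprehensive minimum set may be outstanding.
- **That baselines below 1.5x ULN share the problem.** Their repeat test comes in time; only some work-up triggers sit higher, which is a defensible choice.
- **That the size of the ALT/AST work-up delay can be stated.** It depends on the row reading and on symptom lists that differ: Section 7.1 counts any fatigue, while the Section 8.2.6 footnote requires it to be severe.

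**Conclusion.** The point holds and is minor. For raised-baseline ALP, the repeat and the comprehensive evaluation can both start up to just under 1.0x ULN after the ALP-alone criterion, and 0.5 to just under 1.5x ULN after the ALP-with-symptoms criterion. For ALT/AST with symptoms, the repeat can start up to just under 2.0x ULN late.

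This assumes that baseline lies within the screening limits and, for ALT/AST, that each enzyme is read against its own row. Section 9.4.1 takes baseline as the last value before first dose, so it could drift above the screening limit, which would widen the gap. The protocol gives no count of participants with raised baselines; the number is probably small.

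**What to change.** Keep the baseline multiples in the repeat table and make three edits to Section 8.2.6 at the next amendment:

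1. State that the rows apply to each enzyme separately.
2. Add to the Close Hepatic Monitoring table, for all baselines: *any value meeting a Section 7.1 liver criterion also triggers the 48 to 72 hour repeat, if not already triggered.*
3. In the comprehensive table, change the raised-baseline ALP row to *≥2x baseline or ≥3x ULN, whichever is lower*. Since 2*b* is at least 3.0 whenever *b* is at least 1.5, this works as 3x ULN and matches the row for lower baselines.

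Leave any other comprehensive work-up to the confirmed repeat and the medical monitor consultation. Tying the full work-up to every Section 7.1 criterion would, near the entry limit, require serology and imaging after an ALT/AST rise of only 3.0/2.5 = 1.2x baseline with symptoms, which is a debatable trade.

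The cost is a few extra liver panels and occasional ALP work-ups. At the entry limit the repeat would act at 3.0/2.0 = 1.5x baseline for ALP alone, 2.5/2.0 = 1.25x for ALP with symptoms and 1.2x for ALT/AST with symptoms, but only where Section 7.1 already asks for discontinuation to be considered. Asymptomatic ALT/AST retesting otherwise stays at twice baseline. For ALP with symptoms between 2.5x and 3.0x ULN, the repeat would be called for but the work-up would not, as is already the case for lower baselines.
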